# 4.5 Subject Replacement

Subjects who withdraw from the study post-randomisation will not be replaced.

# 4.6 Subject Restrictions

### 4.6.1 Lifestyle

- Subjects will not be permitted to use any of the following skin care products;-moisturisers, lotions, creams, sunscreen, soaps, cleansing, exfoliation products, moisturising products etc on their legs from the screening visit and for the duration of the study, other than the washout soap bar and moisturising product provided.
- No application of cleansers or water (including no showering/bathing permitted with soaps/shampoo) on the leg sites, within 2 hrs of all instrumental measurements on visit days within this period).
- Subjects must shave their legs 24 hrs before each visit. If desired, the provided cleansing bar can be used as a shaving aid. No other chemical or physical hair removal methods are permitted during the course of the study.
- Subjects may not take any of the medications prohibited in the exclusion criteria throughout the course of the study.
- At all subsequent study visits, subjects must apply the moisturiser provided approximately
  12 hrs before the study appointment and attend the study site with cleansed legs by use of
  soap provided at least 2 hours before instrumental measurements. On study days the AM
  product application will be performed at the site after all assessments have been
  completed.
- Subjects must not smoke or have coffee or any product containing caffeine or alcohol within 4 hrs before the clinic visits and until after the instrumental measurements are completed.
- No hard physical exercises (with heavy sweating), sauna or swimming, 24 hrs before the clinic visit.

• No exposure to artificial ultraviolet (UV) light or cosmetic procedures (includes tanning beds, Intense Pulsed Light (IPL), etc) on the test area for the duration of the study.

# 5 Study Products, Assignment, and Supply Management

# **5.1** Study Products

### 5.1.1 Identity of study products

The following study test preparations will be supplied by the Skin Health Clinical Supplies Department, GSKCH:

• Curel Ultra Healing Lotion for Extra Dry Skin

Other items to be supplied by the Clinical Supplies Department, GSKCH:

• Washout soap bar: Ivory Original soap will be provided to all subjects for use during the entire study duration.

### 5.1.2 Selection of doses

The dose of the moisturiser has been selected to reflect typical consumer usage of this product and also reflects the standard application rate used in clinical studies.

### 5.1.3 Administration

The test sites of both the right and left lower leg's upper and lower area will be marked with a non permanent pen and defined as 10 cm by 12 cm in size (120 cm^2)(as shown in Figure 1). Subjects will be instructed to apply 240 mg of the moisturiser to the lower upper area only (approximately 2 mg cm^-2) on both legs twice daily (in the morning and evening).

The first use of the moisturiser will be under supervision at the study site at Baseline (Day 0). Subsequent use of study products will be applied by the subject at home, as instructed by site staff, or if at a site visit, 30 mins after TEWL measurement. The last moisturiser application will be on the evening before the Day 14 visit.

Subjects will bring their allocated product with them to each post-baseline visit, having applied product 12-16 hrs prior to their appointment time. Subjects will arrive at the study site with cleansed legs 2 hrs before the visit.

### **5.1.4** Dose schedule

Subjects will be required to apply their allocated test product twice a day (morning and evening).

Subjects will need to apply the study product on Day 0, 3, 5, 7, 10 and 12, 30 minutes post TEWL measurement. The first application on Day 0 following all instrumental assessments will be supervised.

Subjects will need to be reminded to bring their study products with them to the study site for the Day 14 visit.

### 5.1.5 Dose modification

No dose modifications are permitted during the study.

### 5.1.6 Product compliance

Subjects will be supervised when using the study product at the Baseline (Day 0) visit, a record of the dispensing and administration of the study products will be kept using the dispensing and administration log and the CRF.

### 5.1.7 Precautions

No special precautions, are necessary provided the study is carried out in accordance with this protocol.

### 5.1.8 Overdosage

An overdose is a deliberate or inadvertent administration of a treatment at a dose higher than specified in the protocol.

Overdose is not likely to occur in this study. Limited quantities of the product will be supplied, and closely monitored by the site for each subject.

# 5.2 Study Product Assignment

### **5.2.1** Randomisation procedure

Not applicable. All subjects will apply the moisturiser provided to each lateral upper leg.

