### **Study Design and Methodology**

This is a single-centre, split-body, single product study designed, to assess barrier repair in two different clinical methods in female subjects with dry skin.

Subjects will give their written consent prior to any study procedures taking place. Eligible subjects will undergo a 7-day washout period, during which only the washout soap provided will be used and also during the rest of the study to cleanse the lower legs.

Subjects must shave their legs 24 hrs before the Baseline visit. At the Baseline visit, only subjects with a trained examiner visual grading score of dryness  $\geq 2$  (moderate) on both lower legs will qualify for the study. In addition, there will be no greater than 0.5 point difference between the right and left leg, and the upper and lower areas on the lateral aspect of each leg.

Each subject's right lower leg and left lower leg's lateral (outer-side) aspect will be divided into two areas, an upper area (treated with moisturiser) and a lower area (untreated). The subject's right lower leg will adopt the "pre-treatment" method and the same subject's left lower leg will adopt the "post-treatment" method (methods are detailed later in this section). The test sites of both the right and left lower lateral leg's upper and lower area will be marked in a non permanent manner and defined as 10 centimetre (cm) by 12 cm in size (120 cm squared (cm²) (as shown in Figure 1).

After the Baseline assessments (Day 0), subjects will be instructed to apply a 240 milligram (mg) sized amount (approximately 2 mg/ (cm²)) of the moisturiser to each marked upper lower lateral area twice a day (morning (AM) and evening (PM)) approximately 8-12 hours (hr) apart for 14 days. There will be no moisturiser application prior to the morning visits, and will then be applied following Transepidermal Water Loss (TEWL) measurement. First on-site application of moisturiser will be supervised by the study site. Subjects must shave their legs 24 hrs before each subsequent site visit.

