### "Pre-treatment" method (Right lateral leg):

From the Baseline visit onwards, initial TEWL measurement at the designated skin sites (Figure 1) as specified in Table 1 will occur. Subsequently twenty tape strips will be taken following D-Squame disc challenge at these sites and time points as designated in Table 1. This will include TEWL measurement after every 5 tape strips (5, 10, 15 and 20 tape strips). Moisturiser application will occur 30 minutes (mins) following the last TEWL measurement on the upper area only. The last moisturiser application will be on the evening before the Day 14 visit.

Figure 1. Lateral aspect of right lower leg marked treatment areas and sites:

[figure not shown]

[figure not shown]
Table 1. Designated skin sites and time point for measurements

Study Day	Day 0	Day 3	Day 5	Day 7	Day 10	Day 12	Day 14
Designated skin sites	1, 8	2, 9	3, 10	4, 11	5, 12	6, 13	7, 14

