### "Post-treatment" method (Left lateral leg):

At the Baseline visit, initial TEWL measurement at the designated skin sites 15 and 16 (Figure 2) will occur. Subsequently twenty tape strips will then be taken following D-Squame disc challenge at these sites, followed by a second TEWL measurement. At all subsequent visits only TEWL will be measured at sites 15 and 16. Moisturiser application will occur 30 mins following the second (Baseline visit) or single (subsequent visits) TEWL measurement on the upper area only. The last moisturiser application will be on the evening before the Day 14 visit.

Figure 2. Lateral aspect of left lower leg marked treatment areas and sites:

Subjects will be acclimatised in a relatively stable environment (temperature 21 degrees centigrade (°C)  $\pm$  2 °C, room humidity 50 %  $\pm$  10 %) for a period of at least 30 mins before measurement of trained examiner visual grading of dryness (Baseline visit) and TEWL measurements.

For the D-Squame discs collected during the "pre-treatment" method, the amount of protein recovered will be measured (by Squamescan) [Lu *et al.*, 2014]. Further analyses of the "pre-treatment" method retained D-Squame discs may be performed within one year of the study report. If this analysis is not performed the tapes will be destroyed. Subjects will consent to this possible additional analysis at screening. Disc destruction will be authorised by GSKCH.

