### **Diagnosis and Main Criteria for Inclusion**

Healthy female, Caucasian volunteers, aged  $\geq 18$  years, with a trained examiner visual grading score of dryness  $\geq 2$  on both lower legs will qualify for the study at the baseline visit. In addition, there will be no greater than 0.5 point difference between the right and left leg, and also between the upper and lower areas on each lateral leg.

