# 8.3 D-Squame Tape Stripping

Tape stripping will be performed at the designated leg skin site for each specific time point by a trained technician using the D-Squame® discs (CuDerm corporation).

A series of D-Squame discs will be gently smoothed sequentially over the test sites applying uniform pressure for 5 seconds with the D500 D-Squame Pressure Instrument® (CuDerm corporation) supplied stamp, using constant pressure to ensure consistent adhesion to the skin. Gripping the white portion of the disc, each disc is then pulled off the skin with one fluent and

® Tewameter is a registered trademark of Courage+Khazaka electronic GmbH

® D-Squame disc is a registered trademark of CuDerm corporation

<sup>® D-Squame Pressure Instrument is a registered trademark of CuDerm corporation

decisive movement. Multiple strips can be done on the same site to move progressively deeper into the stratum corneum. The site being stripped should be accurately marked at the beginning of the process to ensure that subsequent strips are aligned with the first one.

The tape stripping will be performed on the designated leg skin site for each specifictime point. The same specific area will not be restripped within the study. A total of 20 D-squame discs will be taken from the designated leg skin site / time point.

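### The upper area is treated and the lower area is the control in every subject, so the product effect cannot be separated from an upper-lower skin difference

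*Protocol*

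**What the plan says.** The Synopsis (Study Design and Methodology) divides the outer side of each lower leg into "an upper area (treated with moisturiser) and a lower area (untreated". Section 5.1.3 applies the moisturiser to the upper area only, on both legs, and Section 5.2.1 answers the randomisation question with "Not applicable. All subjects will apply the moisturiser provided to each lateral upper leg". Method is tied to leg in the same way: "The subject's right lower leg will adopt the" pre-treatment method, and the left leg takes the post-treatment method.

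On the right leg, Table 1 ("Designated skin sites and time point for measurements") assigns one site pair to each visit for all subjects, from 1/8 on Day 0 to 7/14 on Day 14. Section 8.3 adds: "The same specific area will not be restripped within the study". The left leg differs: "At all subsequent visits only TEWL will be measured at sites 15 and 16".

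Two provisions bear on comparability of the areas. Eligibility allows at most 0.5 dryness grade between the legs and "also between the upper and lower areas on each lateral leg". The models in Section 10.3.3 contain treatment, day, treatment-by-day and subject, with Day 0 covariates. They have no term for area or site.

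**The concern.** A split-body comparison uses each subject as her own control. That removes differences between subjects, but it supports a treatment comparison only if the control skin is exchangeable with the treated skin. Here the two always lie at different heights on the leg, in the same order, so a systematic upper-lower difference in TEWL, in the slope of 1/TEWL on protein, or in the protein intercept enters the treatment estimate in full before adjustment.

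The direction is unknown. Anatomy could make an insensitive measure look responsive, or hide a responsive one. This matters for the study's own purpose: Section 10.3.3 seeks the most sensitive measure, and the Criteria for Evaluation say the results will determine how barrier repair may be measured in later studies. A larger sample would not help, because it only makes a biased contrast more precise.

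**Working it through.** **1. The plan's own figure.** Inputs from Section 10.1: slope mean -3.4e-5, SD 1.4e-5, target difference 1.1e-5; total protein mean 3985 µg, SD 1150, target 880 µg; within-subject correlation 0.5; N=20; two-sided 5%.

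- SD of paired differences = SD × sqrt(2 × (1 - 0.5)) = SD.
- Noncentrality for slope = (1.1/1.4) × sqrt(20) = 3.51; power with 19 df = 91.5%.
- Noncentrality for protein = (880/1150) × sqrt(20) = 3.42; power = 90.1%.
- 1.1/3.4 = 32% and 880/3985 = 22%.

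The stated 90% reproduces. The sample size is not at issue.

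**2. What the contrast estimates.** Let τ be the product effect and δ the upper-minus-lower difference without product. Since treated is always upper, the expected treated-minus-untreated difference is τ + δ. An area indicator would be identical to the treatment indicator, so it cannot be added to the model.

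**3. What the Day 0 covariate removes.** With covariate coefficient β and the same offset δ at Day 0, the adjusted contrast is τ + δ - βδ = τ + (1 - β)δ. The offset disappears only if β = 1. On the right leg Day 0 is read at sites 1/8 and every later visit at another pair. If the offset is δ₀ at 1/8 and δₖ at a later pair, the bias is δₖ - βδ₀, which can change from visit to visit and then appears as treatment-by-day. A gradient shared by both areas moves both members of a pair equally and cancels.

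**4. Illustration for slope.** SE = 1.4e-5/sqrt(20) = 0.313e-5. The offset δ (as a percentage of 3.4e-5) and β are assumptions; the product effect is set to zero. The rejection rate is from the noncentral t with 19 df, for one day's paired test.

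| δ | β | Bias (1 - β)δ | Share of 1.1e-5 | False-positive rate |
|---|---|---|---|---|
| 5% = 0.17e-5 | 0.7 | 0.051e-5 | 5% | 5.3% |
| 5% | 0.3 | 0.119e-5 | 11% | 6.5% |
| 10% = 0.34e-5 | 0.7 | 0.102e-5 | 9% | 6.1% |
| 10% | 0.3 | 0.238e-5 | 22% | 11.2% |
| 20% = 0.68e-5 | 0.7 | 0.204e-5 | 19% | 9.5% |
| 20% | 0.3 | 0.476e-5 | 43% | 30.3% |

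**5. Simulation check, same planning values.** 4,000 runs per setting; the later paired difference is regressed on the Day 0 paired difference, with an assumed correlation of 0.3-0.7 between them.

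- Fixed position, constant offset of 10-20%: 8-27% false positives.
- Fixed position, offset present at the later pair but absent at 1/8: 18-80%.
- Position randomised and area in the model: 4.5-5.4%, with mean bias about zero.

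Section 10.1 gives no planning variability for TEWL change, so no matching figure can be computed for the left leg.

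**The case against.** The best defence has four parts.

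- **Exploratory purpose.** Section 3.2 says the study is not meant to assess product performance, and no product claim follows. This stands as a reason to lower the severity. It does not remove the point, because treated-untreated differences with confidence intervals and p-values are what the methods will be judged on.
- **Matching at entry.** The dryness scale moves in half points (Section 8.1), so a limit of 0.5 is matching to within one step. A reader might take the limit as evidence that upper and lower skin differ; it is a safeguard and shows no such thing. However, it governs a visual grade, not TEWL or protein, and it allows a difference in the same direction in every subject.
- **A sound baseline.** A reader might dismiss the Day 0 covariate as a single noisy reading. It is not: TEWL is taken in duplicate and averaged (Section 8.2), and the slope and intercept rest on five stripping depths (Section 10.3.3). A better baseline can bring β nearer 1, which is why the low end of the range is close to 5%. On the left leg the covariates come from the same sites as the later readings, so what mainly remains there is a repair rate that differs by position.
- **Assumed size.** Neither the offset nor β has a source in the protocol, and the single-day paired test with the unadjusted planning SE is not the planned repeated-measures model. This is correct. A zero offset gives zero bias.

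A reader might also infer that time is confounded with leg position throughout. The protocol does not support that. The left-leg sites are the same at every visit. On the right leg the pairs move together, and the planned inference is between areas within each day, so a common gradient cancels. Day 0 enters only as a covariate, so a drift within one area biases no planned estimate. Figure 1 is not available here, so the geometry of the sites is also unknown.

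**Conclusion.** The aliasing of treatment with upper/lower position is certain: it follows from the layout, applies to both legs and cannot be undone in analysis. The existing safeguards reduce a constant offset without guaranteeing its removal. On the right leg only, an upper-lower difference that varies by site pair also stays in treatment-by-day.

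How much this matters is not known. Under the assumed offsets of 5-20% and β of 0.3-0.7, the slope test rejects in about 5-30% of studies when the product does nothing. This is an illustration, not an estimate of the trial's error rate. It would be wrong to conclude that any observed effect is anatomical, or that the study fails its purpose. The rating is should-fix: the bias is avoidable at little cost, and the study is exploratory.

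**What to change.** In Section 5.2.1, randomise each subject 1:1 to have either the upper or the lower area treated, using the same choice on both legs to limit application errors. In Section 10.3.3, add area (upper/lower) as a fixed effect to the models; it becomes estimable once position varies between subjects. Bring the Synopsis, the study schedule and Section 5.1.3 into line, since they label the upper sites as treated.

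Optionally, vary the right-leg order of sites over visit days between subjects, keeping upper and lower pairs matched, so that differences specific to a site pair are not tied to one day.

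The cost is a randomisation list, subject-specific marking, one extra model term and a small risk of application to the wrong area, since most applications are made at home. No subjects, visits or measurements are added. If the layout is kept, the protocol should state that the treated-untreated difference includes any upper-lower difference, and the results should be read with that limit. This cannot be repaired after data collection.

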### 5.2.2 Blinding procedure and code breaks

Not applicable. All subjects will apply the moisturiser provided to each lateral upper leg.

# 5.3 Study Product Supplies Management

### 5.3.1 Packaging and labelling

Packaging and labelling of all test products will be carried out according to ICH GCP guidelines and will be the responsibility of the Clinical Supplies Department GSKCH.

• Curel Ultra Healing Lotion for Extra Dry Skin in 6 fluid (fl) ounce (oz) (177 ml) containers.

Each study label will contain, but not be limited to, protocol number, directions for storage, emergency contact number. Ivory Original soap bar will be supplied in commercial containers, with labels attached.

All products will be supplied to site and details will be outlined in the shipping manifest. Care should be taken with the supplied study products and their labels so that they are maintained in good condition. It is important that all labels remain intact and legible for the duration of the study. Subjects should be instructed to not remove or deface any part of the study label.

### 5.3.2 Accountability of study supplies

All material supplied is for use only in this clinical study and should not be used for any other purpose.

The investigator or designee will maintain a full record of study product accountability. An Investigational Product Dispensing Log must be kept current and will contain the following information:

- The identification of the subject to whom the study product was dispensed.
- The date(s) and quantity of the study product dispensed to the subject.
- The date(s) and quantity of the study product returned by the subject (if applicable).

The inventory must be available for inspection by the study monitor during the study. At the end of the study, study product supplies will be verified by the monitor. Study product supplies will then be either collected by the study monitor or returned by the investigator or designee after study conduct to the GSK Clinical Supplies Department or designated vendor.

### **5.3.3** Storage of study product supplies

In the study centre, the study product supplies must be stored in compliance with the label requirements in a secure place with limited or controlled access. Study product should be stored at room temperature (15°C to 25°C) away from direct light. A 24 hr/7 day temperature monitoring device will be used to monitor the temperature of the study products. Only the Investigator, designated study nurse/ coordinator or product manager are to have access to the study products.

The subjects will be informed about the storage conditions when the product is dispensed on Day 0.

# 6 Study Schedule

Please refer to the study schedule for a complete listing of the assessments to be performed.

# 7 Screening and Baseline Methods, Measurements and Evaluations

# 7.1 Screening

### 7.1.1 Informed Consent

The investigator, or designee, must obtain written (signed and dated by the subject) informed consent from each subject participating in this study after adequate explanation of the aims, methods, objectives, and potential hazards of the study. The investigator, or designee, must also explain to the subjects that they are completely free to refuse to enter the study or to withdraw from it at any time. Appropriate forms for documenting a written consent will be provided by the investigator or by GSK. The investigator, or designee, should sign and date the consent form to confirm that the consent process was completed correctly. The subject will be provided with a copy of their signed and dated consent form and any other written information which they should be instructed to retain. Subjects will give consent to the collection of the D-squame discs and the potential further analyses of the "pre-treatment" D-Squame discs within one year of the study report. If this analysis is not performed the tapes will be destroyed. Disc destruction will be authorised by GSKCH.

If, during a subject's participation in the study, any new information becomes available that may affect the subject's willingness to participate in the study, each ongoing subject should receive a copy of this new information and be re-consented into the study. Subjects should be provided with a copy of the signed and dated amended consent form.

